7.2.2. Efficacy

7.2.2.1. Intercurrent Event (IE)

IE1: Study drug discontinuation for major worsening of primary Sjögren's syndrome.

IE2: Increase or initiation of authorized medication for pSS.

IE3: Study drug discontinuation for AE related to study drug.

IE4: Study drug discontinuation for other reasons (non-medical reason, AE not related...).

IE5: Switch of treatment group (error of dispensation).

IE6: Decrease or stop of authorized medication for pSS.

For all efficacy endpoints, a flag for each intercurrent event (IE) will be created to identify the values collected post-IE vs the values before or on the IE date. As a reminder, the IE date is the date of the start of IE.

One global IE flag will be derived to determine which IE occurs first. In case a patient is concerned by several IEs, the first event will be considered. If several IE occurred the same day, IE will be considered to be more conservative in the following order: IE1; IE2; IE3; IE4; IE5, IE6.

Study drug discontinuation for major worsening of primary Sjögren's syndrome (IE1) is defined as follow:

- AE related to pSS leading to study drug discontinuation.

Increase or initiation of authorized medication (IE2) is defined as follows:

- Any increase or initiation of a new dose of corticosteroids (oral prednisone or equivalent) within 4 weeks prior to W013 visit.
- Any intramuscular, IV, or intra-articular corticosteroids within 4 weeks prior to W013 visit.
- Any increase or initiation of new dose of topical corticosteroids within 2 weeks prior to W013 visit.

CL2-95011-001 - Statistical Analysis Plan | VV-TMF-116033 | 2.0

- Any increase or initiation of new dose of antimalarials (e.g. chloroquine, hydroxychloroquine, quinacrine) after randomisation (W000).
- Any increase or initiation of new dose of methotrexate after randomisation (W000).
- Any change in route of administration of methotrexate within 4 weeks prior to W013 visit.
- Any increase or initiation of new dose of regularly scheduled Non-steroidal anti-inflammatory drugs (NSAIDs) within 2 weeks prior to W013 visit.
- Any increase or initiation of new doses of cevimeline or oral pilocarpine within 2 weeks prior to W013 visit.
- Any increase or initiation of new doses of Ocular topics (excluding artificial tears, gels, lubricants, antibiotherapy) within 90 days prior to W013 visit.
- Required regular use of medications known to cause dry mouth/eyes as a regular and major side effect, and which have not been on a stable dose for at least 30 days prior to W013.

Study drug discontinuation for AE related to study drug (IE3) is defined as follow:

- AE related to IMP leading to study drug discontinuation.

Study drug discontinuation for other reasons (non-medical reason, AE not related...) (IE4) is defined as follow:

- Patients who did not receive IMP infusion neither at this visit nor at the following ones without any AE related to pSS or related to IMP leading to study drug discontinuation.

Decrease or stop of authorized medication for pSS (IE6) is defined using the same time windows and definitions as IE2.

The lists of the considered ATC codes for IE2 are the excel files:

- 2602.0 Systemic and local treatments containing corticosteroids DDB320221.
- 4306.0 Treatments containing antimalarial DDB320221.
- 4302.0 Treatments containing methotrexate DDB320221.
- 3700.2 Non-steroids antinflammatory drugs (NSAIDS) DDB320221.
- 4309.0 Treatments containing cevimeline and pilocarpine DDB320221.
- 4324.0 Ocular topics for S95011 DDB320221.
- 4382.1 Drugs known to induce dry mouth and dry eyes DDB320221.

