10.1.2.4. Efficacy analysis

10.1.2.4.1. Primary estimand based on the ESSDAI

The primary estimand of interest is the effect of the initially randomised treatments on the clinical disease activity in all patients assuming non-occurrence of intercurrent events. The motivation for this choice is to assess at this proof-of-concept stage the full efficacy potential, that is, the pharmacologic effect of the S95011 if all patients adhere to it (without any intercurrent events).

The attributes of the primary estimand are defined as follow:

- Treatment: S95011 or placebo
- Population: RS
- Variable: change in ESSDAI total score from baseline to W13 (primary efficacy endpoint).
- Summary measure: difference in means between treatments.
- Intercurrent events (IE):
 - change or initiation of unauthorised medication
 - study drug discontinuation for major worsening of primary Sjögren's syndrome or AE related to study drug
 - study drug discontinuation for other reasons (non-medical reason, AE not-related...)
 - unexpected others events having a major impact on the pharmacologic effect evaluation (They will be defined at the latest in the final version of the SAP).

The rate of IEs is assumed to be below 10%. They will be handled by a hypothetical strategy to estimate what the outcome would have been at the designated time point if no IE would have occurred through that time point, considering that patients with IE would have efficacy outcomes as patients, in their treatment group, who continue their randomised treatment without IE.

10.1.2.4.1.1. Primary analysis

The primary analysis for the primary estimand will be conducted using only data obtained prior to IEs. Values post IE will not be taken into account and will be imputed according to the MAR assumption (multiple imputation by treatment group). This is aligned with the primary estimand and the hypothetical strategy.

S95011 will be compared to placebo on the primary efficacy endpoint in the RS, using a General Linear Model including the fixed, categorical effect of treatment and randomisation stratification factors (*rando_factor*) as well as the continuous fixed covariate of baseline value.

GENERAL LINEAR MODEL: change = baseline rando_factors treatment

The assumptions underlying the model, as for instance, the normality and homoscedasticity of residuals and detection of outliers, will be checked.

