4.3.1. Primary efficacy estimand

The primary estimand of interest is the effect of the treatments on the clinical disease activity in all patients assuming non-occurrence of intercurrent events (IE). The motivation for this choice is to assess at this proof-of-concept stage the full efficacy potential, that is, the pharmacologic effect of the S95011 if all patients adhere to it (without any intercurrent events).

The attributes of the primary estimand are defined as follow:

- **Treatment:** S95011 or placebo.
- **Population:** RS.
- **Variable:** change in ESSDAI total score from baseline to W013 (primary efficacy endpoint).
- **Summary measure:** difference in means between treatments.
- **Intercurrent events (IE):**
 - IE1: Study drug discontinuation for major worsening of primary Sjögren's syndrome.
 - IE2: Increase or initiation of authorized medication for pSS.
 - IE3: Study drug discontinuation for AE related to study drug.

- IE4: Study drug discontinuation for other reasons (non-medical reason, AE not related...).
- IE5: Switch of treatment group (error of dispensation).
- IE6: Decrease or stop of authorized medication for pSS.

The rate of IEs is assumed to be below 10%. They will be handled by a hypothetical strategy to estimate what the outcome would have been at the designated time point if no IE would have occurred through that time point, considering that patients with IE would have efficacy outcomes as patients, in their treatment group, who continue their treatment without IE.

Note: In case a patient is concerned by several IEs, the first event will be considered. If several IE occurred the same day, IE will be considered to be more conservative in the following order: IE1; IE2; IE3; IE4; IE5, IE6.

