Missing data/intercurrent events handling: the primary analysis for the primary estimand will be conducted using only data obtained prior to IEs. Observed post IE values will not be used in the primary analysis. Post IE values will be imputed according to the MAR assumption (multiple imputation by treatment group). This is aligned with the primary estimand and the hypothetical strategy. Missing data not linked to intercurrent events will be imputed according to the MAR assumption with a multiple imputation by treatment group. The imputation method is detailed below and in [Appendix 7.3.1](#). A patient with all visits missing or only baseline missing will not be considered in the analysis.

Multiple imputation inference involves 3 consecutive phases.

1/ Imputation step:

A total of 100 imputed complete data sets will be generated.

The imputation step for missing data as well as data considered as missing for the primary analysis due to the strategy used to handle intercurrent event will be the same and applied to data with a monotone pattern. For all patients, the regression method (adjusted on randomisation stratification factors, baseline and considering all longitudinal data of planned visits) will be used separately for each treatment arm to impute missing data (*i.e.* based on patient completers under corresponding treatment arm) under MAR approach.

It is of note that for missing data with an arbitrary missing pattern, the first imputation step might be preceded by one MI approach based on MCMC method using baseline and all longitudinal data by treatment groups.

If the regression method for imputation is not running due to too few patients in the stratas, the model mentioned above will be modified. Thus, the two stratification factors in the model will be replaced by the following composite factor: baseline intake of oral corticosteroids or antimalarial or both (yes/no). If the model is still not running with the stratification factor in two classes, then the stratification factor will not be considered.

2/ Analysis step:

The same model as [1] (described above) will be applied to each of the 100 imputed datasets.

3/ Combination step:

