Regarding the estimand framework, some changes has been made between the protocol and the SAP on intercurrent events. Indeed, “*study drug discontinuation for major worsening of primary Sjögren’s syndrome or AE related to study drug*” has been split into two independent IEs as “*study drug discontinuation for major worsening of primary Sjögren’s syndrome*” (IE1) is considered more impacting than “*Study drug discontinuation for AE related to study drug*” (IE3). Thus, for sensitivity analyses, it is has been decided to handle data post the IE1 using a reference based multiple imputation (“jump to placebo” approach) while data post the IE3 are considered moderately bad outcome and will be handled using a reference based multiple imputation (“copy increment in reference” approach). In the same line, intercurrent event “*change or initiation of unauthorised medication*” from the protocol has been split into “*Increase or initiation of authorized medication for pSS*”(IE2) and “*Decrease or stop of authorized medication for pSS*” (IE6) (the unauthorized part being necessarily linked to discontinuation for major worsening this part is already handled by IE1). Here again, IE2 having more impact than IE6, post IE data will be handled using different method (respectively reference based multiple imputation “copy increment in reference” and MAR approaches) for sensitivity analyses. Finally, IE5 “*Switch of treatment group (error of dispensation)*” has been added to handle the case of the patient having a treatment switch discussed above (MAR approach).

For all efficacy analyses, it has been specified that if the regression or the imputation model does not run due to too few patients in the stratas, the four classes randomisation stratification factor will be replaced by a 2 classes composite factor: baseline intake of oral corticosteroids or antimalarial or both (yes/no). If the model is still not running, then the stratification factor will not be considered.

Finally, for the treatment policy efficacy analysis, it has been considered sufficient to consider only responders in ESSDAI defined as patients with an improvement of at least 3 points and responders in ESSPRI defined as patients with an improvement of at least 1 point.

The salivary gland tissue will not be described because of the very small number of available biopsies collected at W013.

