7.3.3. Imputation step for main analysis on primary endpoint

We will implement a standard multiple imputation method for handling missing data due to any kind of IE as well as missing data for other reasons.

Standard multiple imputation: this method (Rubin, 1987) replaces each missing value with a set of plausible values that represent the uncertainty about the right value to impute. Each value is a Bayesian drawn from the conditional distribution of the missing observation given the observed data, made in such a way that the set of imputation properly represents the information about the missing value that is contained in the observed data for the chosen model.

The multiply imputed data sets are then analysed by using standard procedures for complete data and combining the results from these analyses, based on the change from baseline.

Multiple imputation inference involves **3 consecutives phases** (phase 1: imputation step, phase 2: analysis step and phase 3: combination step).

Phase 1: Imputation step

To guarantee the reproduction of results, the seed will be fixed at 95011.

Step 1:

First, data collected post IE should be considered as missing (use flag derived in ADAM). In case of patient with several events (IE1="Y" and IE2="Y"...), the first one will be considered and all the values after (strictly) will be considered as missing. All intermittent missing data (*i.e.* with an arbitrary missing pattern) will be first imputed using a MI approach based on MCMC method using baseline and all longitudinal data by treatment groups, in case the initial dataset has not a strict monotone missing pattern.

A total of 100 imputed partially completed datasets will be generated. This dataset will serve as a basis for Step 2 (*DATA BASIS*). For the following step, the entry dataset will be sorted by imputation, by treatment and by USUBJID.

Step 2:

In this sequence, remaining missing data of *DATA_BASIS* will be imputed. For all patients with missing data with or without an IE:

- To impute those missing data, all data (*DATA_BASIS*) will be considered in order to benefit of all data available at each visit.

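### The intercurrent-event windows in SAP 7.2.2.1 miss an oral corticosteroid or regular NSAID change made early in treatment and still in use at W013

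*SAP*

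**What the plan says.** SAP 4.3.1 lists "IE2: Increase or initiation of authorized medication for pSS" and a matching event for decreases and stops (IE6), neither with a time limit. The operational rules are in SAP 7.2.2.1:

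- Oral corticosteroids: "Any increase or initiation of a new dose of corticosteroids (oral prednisone or equivalent) within 4 weeks prior to W013 visit".
- NSAIDs: "Any increase or initiation of new dose of regularly scheduled Non-steroidal anti-inflammatory drugs (NSAIDs) within 2 weeks prior to W013 visit".
- IE6: "Decrease or stop of authorized medication for pSS (IE6) is defined using the same time windows and definitions as IE2".
- Antimalarial and methotrexate dose increases or initiations count at any time from randomisation on.

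SAP 4.3.1.1 states the consequence of a flag: "Observed post IE values will not be used in the primary analysis". SAP 7.3.3 adds that, for a patient with several events, "the first one will be considered and all the values after (strictly) will be considered as missing". SAP 6 separates the two medication events: "Here again, IE2 having more impact than IE6, post IE data will be handled using different method". In the sensitivity analysis, S95011 patients with IE2 are imputed by copy increments and those with IE6 under MAR.

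Protocol 6.3 requires permitted background drugs, including oral corticosteroids up to 10 mg/day prednisone equivalent and NSAIDs, to be kept on the baseline regimen for the whole treatment period. It also requires dosage changes to be entered in the e-CRF. Exclusion criterion 31 (Protocol 5.2) uses the same 4-week and 2-week windows, counted back from W000.

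**The concern.** The windows test whether background treatment was stable just before an assessment. That suits entry, where criterion 31 needs a settled baseline. The primary endpoint, however, is a change from W000, and a dose that has been stable for four weeks before W013 may not have been in use at W000.

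The primary estimand asks what would have happened without intercurrent events. If an early change is unflagged, the W013 value observed on altered background treatment is used as though nothing had happened. The linear model does not correct for this: it adjusts for baseline ESSDAI and for baseline corticosteroid and antimalarial intake only. The sensitivity analysis uses the same flags, so it cannot expose the problem.

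There is also a typing problem. A dose raised early and then reduced inside the window is caught, but it is dated at the reduction and classed as IE6. The sensitivity analysis then imputes it under MAR, although the change relative to W000 was an increase.

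**Working it through.** **1. Can another event catch the case?** Take a patient who starts or raises an authorised oral corticosteroid dose at W005, keeps it to W013 and stays on study drug. IE1, IE3 and IE4 require study drug discontinuation, and IE5 is a dispensing error. IE2 needs the change to fall inside the final 4 weeks. No flag is set.

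**2. Uncovered time** (nominal visits, W013 = day 91).
- Oral corticosteroids: 91 − 28 = 63 days, about W000 to W009.
- Regular NSAIDs: 91 − 14 = 77 days, about W000 to W011.

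**3. The plan's own operating characteristics** (SAP 1.2: 30 and 15 patients, SD 6, one-sided 10%, and an estimated difference of at least 3).
- SE = 6 × √(1/30 + 1/15) = 1.897.
- Significance boundary = 1.302 × 1.897 = 2.47 (t, 43 df). This is below 3, so the 3-point criterion governs.
- P(success) = 1 − Φ((3 − d)/1.897), where d is the true difference: 5.7% at d = 0, 14.6% at d = 1, 50.0% at d = 3 and 70.1% at d = 4. The plan gives around 5%, below 14% for differences under 1 point, about 50% and about 70%, so its figures reproduce to within a point.

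**4. Illustration of the shift.** The documents give no drug effect on ESSDAI. Assume that the changed drug lowers the articular domain (weight 2, Protocol Appendix 3) by one or two levels, that is, 2 to 4 points. Let the true difference be 4.

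| Unflagged patients | Shift in difference | Difference | P(success) |
|---|---|---|---|
| 1 of 15 placebo, 2 points | −2/15 = −0.13 | 3.87 | 67.6% |
| 1 of 15 placebo, 4 points | −4/15 = −0.27 | 3.73 | 65.0% |
| 1 of 30 S95011, 2 points | +2/30 = +0.07 | 4.07 | 71.3% |
| 1 of 30 S95011, 4 points | +4/30 = +0.13 | 4.13 | 72.5% |
| 1 of 15 and 2 of 30, equal effect g | 2g/30 − g/15 = 0 | 4.00 | 70.1% |

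The shift can go either way, and it vanishes when rates and effects are equal in the two arms.

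**The case against.** The windows may be deliberate. The label in SAP 4.3.1 is short, and SAP 4.3 refers the reader to the appendix for definitions, so 7.2.2.1 can be read as supplying the operational rule, not contradicting it. The list differs by drug, and a short window avoids discarding W013 after a brief early course that has worn off. The whole-period count for antimalarials and methotrexate may itself come from the entry windows, since 16 weeks exceeds the 13-week period and 12 weeks nearly fills it. The SAP gives no reason either way.

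This argument protects changes that were reversed before the window. It does not cover a regimen still in use at W013, which breaches Protocol 6.3 and still affects a change measured from W000.

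A reader might also cite the protocol's own event list as proof that authorised changes were meant to count at any time. It does not show that: the protocol names "change or initiation of unauthorised medication", which is a different event. The authorised-dose events first appear in the SAP.

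The occurrence of such changes would be partly visible in the deviation tables (SAP 4.1.2) and the concomitant-treatment tables (SAP 4.2.2). The latter are by ATC code and preferred name, so they do not separate a dose changed since W000 from a stable one, and neither table alters the estimate.

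**Conclusion.** The gap is real and minor. For oral corticosteroids and regularly scheduled NSAIDs, the flag rule does not match the estimand it serves, the exclusion of post-event data, or the stability rule in Protocol 6.3. These passages need to be reconciled.

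Three stronger readings are not supported.

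- The uncovered 63 and 77 days are calendar time, not a share of patients or of changes.
- The documents do not show a bias against or in favour of S95011. Stacking three unflagged placebo patients at 4 points each, with none on S95011, would cut the difference from 4 to 4 − 12/15 = 3.20 and the chance of success to 54.2%. That needs an imbalance the documents give no reason to expect.
- The gap does not extend to antimalarial or methotrexate dose changes, which count from W000. Corticosteroids above 10 mg/day are a separate case: they are prohibited and should lead to study drug discontinuation, which is an intercurrent event if that rule is followed.

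What can be said is that one unflagged patient in one arm moves the difference by 0.07 to 0.27 points against an SE of 1.90, under the assumed 2 to 4 point effect. Because the 3-point criterion binds, any such shift acts directly on the success rule.

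**What to change.** Keep the existing windows, so that changes reversed before the window stay unflagged. In addition, flag IE2 or IE6 when the oral corticosteroid or regular NSAID regimen in use at any time inside the window differs from W000. Date the event at the start of that change and type it by the direction of the difference from W000.

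Use this one definition for every efficacy endpoint: ESSDAI, ESSPRI, their composite, STAR, CRESS and the rest. Endpoint-specific rules should be avoided. SAP 7.2.2.1 derives the flags for all efficacy endpoints, and the ESSDAI/ESSPRI composite would otherwise combine components imputed under different definitions. Report the number of patients reclassified by arm. If unblinding has occurred, run this as a labelled post hoc sensitivity analysis. This concerns analysis flags only and proposes no treatment rule.

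The work is SAP wording and a re-derivation of two flags from dose changes already in the e-CRF. The statistical cost is a few more imputed W013 values. Where the change precedes W004 (28 of the 63 or 77 uncovered days), the W004 value is lost too and imputation rests on baseline and strata. If one placebo and two S95011 values carry no information, SE = 6 × √(1/28 + 1/14) = 1.964, and the chance of success at a true difference of 4 falls from 70.1% to 69.5%. If W004 is kept, with an assumed W004–W013 correlation ρ of 0.3 to 0.7 (effective n of about 28 + 2ρ² and 14 + ρ²), it is 69.5% to 69.8%. In the balanced case this small loss buys no reduction in bias.

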7.2. Methods and measurement times

- **ESSDAI (EULAR Sjögren Syndrome Disease Activity Index):** ESSDAI is a physician-administered clinical index used to evaluate systemic disease activity. The instrument contains 12 organ-specific domains contributing to disease activity (*i.e.*, organ systems: cutaneous, respiratory, renal, articular, muscular, peripheral nervous system (PNS), central nervous system (CNS), haematological, glandular, constitutional, lymphadenopathic, biological). For each domain, features of disease activity are scored in 3 or 4 levels according to their severity. These scores are then summed across the 12 domains in a weighted manner to provide the total score. The maximum theoretical score is 123 ([Appendix 3](#)).

During screening, ESSDAI total score should be ≥ 6 , with at least 6 points within the 7 following domains: constitutional, lymphadenopathy, glandular, articular, cutaneous, hematologic and biologic.

Then, ESSDAI will be applied to the study patients at ASSE, W000, W004 and W013.

The approximative total duration of the measurement is 30 minutes.

This scale must be administered by a trained clinician. The training will be performed before the inclusion of any patient in the site.

Over the course of the study, the ESSDAI should be completed by the same trained investigator for a given patient (insofar as possible). If there is a change in site personnel over the course of the study, new investigators must be trained and certified prior to performing the ESSDAI.

At each ESSDAI assessment, cryoglobulins measurement will be performed locally and the result will be used for ESSDAI scoring. In case of presence of cryoglobulinaemia, cryoglobulin will be identified (Type I, II or III) and reported in e-CRF. Cryoglobulin result obtained from a previous sampling performed within 1 month before screening visit could be used for ESSDAI scoring at screening.

In addition, immune panel (C3 and C4 complement fractions, CH50 (or CH100), quantitative immunoglobulins, and immunofixation electrophoresis) will be assessed at each visit with ESSDAI assessment for exploratory endpoint, by a central laboratory. The results will be provided to the investigator and used for ESSDAI scoring (see [Section 9.5.1](#)).

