1.2. Determination of sample size

The following efficacy criteria are defined:

- A statistically significant reduction in ESSDAI at W013 in the S95011 group compared to placebo, at the one-sided 10% significance level.
- An estimated mean reduction in ESSDAI in the S95011 group to be 3 points or greater than placebo. The decrease of 3 points was chosen because it is considered as clinically minimal relevant decrease ([Seror et al, 2016](#)).

Targeted sample size

With 45 patients in the primary analysis of the primary estimand (30 in the S95011 group and 15 in the placebo group), the study would have around 5% chance of having a false-positive result, *i.e.*, of meeting both the efficacy criteria when the true difference between S95011 and placebo is zero. Additionally, the chances of meeting both the efficacy criteria remain below 14% for true differences between S95011 and placebo of less than 1 point.

The study would have approximately 70% chance of meeting both the efficacy criteria, when the true difference between S95011 and placebo is 4 points. In case the true difference between S95011 and placebo is only 3 points, the study would have approximately 50% chance of meeting both the efficacy criteria. These calculations assume that the primary efficacy endpoint, change from baseline in ESSDAI, follows a normal distribution with a standard deviation of 6. This estimate of the standard deviation is based on some clinical studies (Fisher *et al*, 2020, UCB5857, RO5459072) in patients with primary Sjögren's syndrome in which the observed standard deviation ranged from around 4 to 6.

Blinded standard deviation reassessment

The similar operational characteristics (false-positive and right-positive rates) are obtained with 20 patients in S95011 group and 10 patients in placebo group under assumption of an overall standard deviation of primary efficacy endpoint of 5. So only if the recruitment is much longer than expected, when 30 patients will have completed the 13-week treatment period, the overall standard deviation of the primary endpoint on non-comparative data could be calculated. If the value is less or equal to 5, the sponsor could stop the patient recruitment, considering that the number of patients is sufficient to meet both efficacy criteria. This potential adaptation has very little or no impact on the probability of having a false-positive result (Kieser, 2003).

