4.3.1.1. Primary analysis

Primary analysis will be done on RS.

Definition: the primary efficacy endpoint is defined as the change from baseline to W013 in ESSDAI total score. The ESSDAI total score is calculated as the weighted sum of 12 items of the scale in ClinTrial database.

Primary analysis: to assess the efficacy of S95011 (750 mg) as compared to Placebo on change from baseline to W013 in ESSDAI total score after a 13-weeks treatment, using a General Linear Model including the fixed, categorical effect of treatment and randomisation stratification factors (rando_factor) as well as the continuous fixed covariate of baseline value. The randomisation stratification factors are baseline intake of oral corticosteroids (yes/no) and baseline intake of antimalarial (yes/no)

GENERAL LINEAR MODEL: $change = baseline + rando_factors + treatment$ [1]

The assumptions underlying the model, as for instance, the normality and homoscedasticity of residuals and detection of outliers will be checked. The assumptions of normality and homoscedasticity of residuals will be investigated using some graphs and descriptive statistics. The detection of outliers will be done using graphics.

If the model is not running due to too few patients in the stratas, the model mentioned above will be modified. Thus, the two stratification factors in the model will be replaced by the following composite factor: baseline intake of oral corticosteroids or antimalarial or both (yes/no). If the model is still not running with the stratification factor in two classes, then the stratification factor will not be considered.

Statistical hypotheses:

Let μ_0 and μ_1 be the population means of the change from baseline in ESSDAI total score at W013 (primary endpoint) under placebo and S95011, respectively.

The statistical hypotheses that will be tested are:

$$H_0: \mu_0 \geq \mu_1 \text{ (S95011 is not superior to placebo)}$$

versus

$$H_1: \mu_0 < \mu_1 \text{ (S95011 is superior to placebo)}$$

The type I error of the statistical tests will be set at 10% for unilateral situation, which is consistent with the objective of demonstrating the superiority versus placebo.

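### One intercurrent-event list serves every endpoint, so changes in dryness-related drugs discard observed ESSDAI values without a stated reason

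*SAP*

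**What the plan says.** SAP 7.2.2.1 sets the scope of the flags: "For all efficacy endpoints, a flag for each intercurrent event (IE) will be created to identify the values collected post-IE". One global flag then records whichever event comes first. IE2 is an increase or initiation of authorised medication for primary Sjögren's syndrome (pSS). IE6 is a decrease or stop, with the same items and windows.

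Three IE2 items concern dryness:

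- **Ocular topicals:** "Any increase or initiation of new doses of Ocular topics (excluding artificial tears, gels, lubricants, antibiotherapy) within 90 days prior to W013 visit".
- **Saliva stimulants:** an increase or new dose of cevimeline or oral pilocarpine within 2 weeks before W013.
- **Dryness-causing drugs:** "Required regular use of medications known to cause dry mouth/eyes as a regular and major side effect", where the dose has not been stable for at least 30 days before W013.

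For the primary ESSDAI analysis, SAP 4.3.1.1 says: "Observed post IE values will not be used in the primary analysis". SAP 7.3.3 sets every value strictly after the first event to missing and imputes it under missing-at-random (MAR), by arm. In the sensitivity analysis (SAP 4.3.1.2 and 7.3.4), values after IE2 on S95011 are imputed by copy increments in placebo; IE6 stays under MAR.

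Protocol 7.2 says of ESSDAI: "The instrument contains 12 organ-specific domains contributing to disease activity". Appendix 3 lists the domains. None scores dryness, tear production, ocular staining or salivary flow, and the glandular domain scores swelling.

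**The concern.** An intercurrent event belongs in a hypothetical estimand when it would disturb the interpretation of the variable being analysed. Dryness drugs plausibly disturb Schirmer, ocular staining (OSS), sialometry and ESSPRI. Nothing in the documents says that they disturb ESSDAI. Where Protocol 6.3 shields assessments from saliva stimulants, eye drops, artificial tears and artificial saliva, it names only the Schirmer test and sialometry.

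Two features suggest that the list was not built for ESSDAI. The three windows (90 days, 2 weeks, 30 days) match those of exclusion criterion 31, with W013 in place of W000. And drugs that cause dryness are not medication for pSS, which is what IE2 is called; Protocol 6.3 lists them separately from the permitted pSS medications.

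At stake are observed primary-endpoint values in a small trial, and the clarity of the primary estimand. In the sensitivity analysis, an S95011 patient with such a change is also given placebo-like increments, for a reason with no stated link to systemic activity.

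**Working it through.** **Inputs.** From SAP 1.2: "With 45 patients in the primary analysis of the primary estimand (30 in the S95011 group and 15 in the placebo group"), and an ESSDAI change that "follows a normal distribution with a standard deviation of 6". From SAP 4.3.1.1: "The type I error of the statistical tests will be set at 10% for unilateral situation". SAP 1.2 also requires an estimated difference of at least 3 points.

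**Formulas.** SE = 6 × √(1/n₁ + 1/n₀). Chance of success at true difference d = P(estimate ≥ max(3, 1.2816 × SE)), with the estimate normal around d.

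**The plan's own figures.** SE = 6 × √(1/30 + 1/15) = 1.897. Since 1.2816 × 1.897 = 2.43, the 3-point criterion governs.

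| True difference | Stated | Computed |
|---|---|---|
| 0 | around 5% | 5.7% |
| 1 | below 14% (for less than 1) | 14.6% |
| 3 | about 50% | 50.0% |
| 4 | about 70% | 70.1% |

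These agree closely enough to use the method. A version based on the t distribution gives the same values to within 0.1 point.

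**Windows.** W013 is day 91 and W004 is day 28. ESSDAI is scored at W000, W004 and W013.

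- Ocular topicals: 91 − 90 = day 1, so the window covers nearly the whole treatment period. A change before W004 removes both post-baseline ESSDAI scores.
- Dryness-causing drugs: 91 − 30 = day 61, so only W013 can be lost.
- Cevimeline or pilocarpine: 91 − 14 = day 77, so only W013 can be lost.
- For contrast, the oral corticosteroid item has a 4-week window: 91 − 28 = day 63. An oral corticosteroid increase at week 3 (day 21) does not trigger IE2 and removes nothing. An ocular topical started that day removes W004 and W013.

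**Loss of precision.** The documents give no rate for these three items. Assume that 2 to 6 of 45 patients are flagged only for them and that imputation recovers no information.

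| Patients lost | Arms | SE | Rise | Success at true 0 | Success at true 4 |
|---|---|---|---|---|---|
| 0 | 30/15 | 1.90 | – | 5.7% | 70.1% |
| 2 | 28/15 | 1.92 | 1% | 5.9% | 69.9% |
| 2 | 29/14 | 1.95 | 3% | 6.2% | 69.6% |
| 6 | 26/13 | 2.04 | 7% | 7.0% | 68.8% |

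For the last row, 6 × √(1/26 + 1/13) = 2.038. The chance at 4 points is Φ(1/2.038) = 68.8%, and at zero it is 1 − Φ(3/2.038) = 7.0%.

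**Bias.** An illustrative simulation used a true difference of 4 and no help from W004, and let patients with a worse ESSDAI change be more likely to be flagged. All rates and correlations are assumptions.

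| Loss, S95011 / placebo | Correlation 0 | 0.3 | 0.5 |
|---|---|---|---|
| 10% / 10% | 4.0 | 4.0 | 4.0 |
| 10% / 20% | 4.0 | 3.7 | 3.5 |
| 5% / 25% | 4.0 | 3.4 | 3.1 |

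With no correlation there is no bias. In these runs a visible shift needed both a correlation and unequal loss between arms.

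**The case against.** The best defence is Protocol 6.3. It requires a stable regimen of salivary stimulants, cyclosporine eye drops, lifitegrast and dryness-causing drugs throughout treatment. The primary estimand asks for the effect if nobody has an intercurrent event, so counting a departure from the required regimen is coherent. This explains where the items come from. It does not explain why a departure should void an ESSDAI score, or why an ocular change at week 3 counts when an oral corticosteroid increase at week 3 does not.

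Second, the treatment-policy ESSDAI estimand in SAP 4.3.3 keeps all observed values. That stands, and it means that the data are not lost from every analysis. But that estimand is not primary, and it ignores all events together, so it cannot isolate these items.

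Third, copy increments is a deliberate stress test that preserves the benefit already obtained. That is fair for a late event. For an ocular change before W004, the last retained score is baseline, so there is no benefit to preserve.

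A reader might go further and infer that these drugs cannot affect ESSDAI. The documents do not say so: code lists 4324.0 and 4382.1 are named but their contents are not shown, and the glandular domain does score lachrymal and salivary gland swelling. Nor is every eye drop or drying drug caught. Artificial tears, gels, lubricants and antibiotics are excluded, and drying drugs count only if use is regular, dryness is a regular and major side effect, and the dose was unstable within 30 days.

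**Conclusion.** The mechanism is clear in the current text. Observed ESSDAI values are discarded in the primary analysis after changes that are not expected to affect ESSDAI, and no justification is given.

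The loss of precision is small. With 2 to 6 patients lost, the standard error rises by 1% to 7%, success at a true 4 points falls by at most about 1 percentage point, and the chance at a true zero rises by at most about 1.4 points (5.7% to about 7%). This rests on an assumed event count, loss roughly in proportion to the 2:1 allocation, and no recovery through imputation. The last is pessimistic for the two items that leave W004 intact. The upper end, 6/45 = 13%, already exceeds the rate below 10% that SAP 4.3.1 assumes for all intercurrent events together.

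A reader might infer a serious power loss or a biased primary estimate. The documents support neither. Bias arises only if the loss is related to outcome, and they hold no data on that. The case for change is that observed primary data should not be dropped without a reason, and that the remedy is nearly free.

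**What to change.** In SAP 7.2.2.1, make the IE2 and IE6 flags endpoint-specific.

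- **ESSDAI** (change, responder analyses, and the ESSDAI component of the ESSDAI and ESSPRI composite): do not treat changes limited to the three dryness items as intercurrent events. First have the sponsor's clinicians confirm from the code lists that no listed product could plausibly alter an ESSDAI domain.
- **ESSPRI** (including its component of the composite), **Schirmer, OSS, salivary flow, PGA, PhGA, STAR and CRESS:** keep the full list.
- **Reporting:** give intercurrent-event counts by item and arm.

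The cost is SAP wording, one extra flag, and different event lists across endpoints, which the report must explain. No new data are needed.
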